# 5.3 Lost to follow up Procedure

A subject will be considered lost to follow-up if he or she repeatedly fails to return for scheduled visits and is unable to be contacted by the study site.

The following actions must be taken if a subject fails to return to the clinic for a required study visit:

- The site must attempt to contact the subject and reschedule the missed visit as soon as possible and counsel the subject on the importance of maintaining the assigned visit schedule and ascertain whether or not the subject wishes to and/or should continue in the study.
- Before a subject is deemed lost to follow up, the Investigator or designee must make every effort to regain contact with the subject (where possible, tele-health appointment and, if necessary, a certified or registered letter to the subject's last known mailing address or local equivalent methods). All these contact attempts should be documented in the subject's medical record.
- Should the subject continue to be unreachable, he/she will be considered to have withdrawn from the study.

## 5.4 Screening Failure

Screening failures are defined as subjects who consent to participate in the clinical study but are not subsequently entered in the study. Screen failure data will be captured in EDC.

Re-screening/re-assessment outside the screening period will be possible on a case-by-case basis following Sponsor approval. Subjects allowed to be re-screened will be assigned a new screening number such subjects will be determined to be permanent screen failures after the second screening determines a subject is ineligible.

## 5.5 Classification of Subjects Who Discontinue the Study

For any subject who discontinues the study prior to completion, the most significant reason for early termination will be checked in the eCRF. Reasons are listed below from the most significant to the least significant:

Adverse Event	To be used when the subject is permanently terminated from the study because of an AE (including an SAE), as defined in Section 9.1.1
Lost to Follow-up	To be used when the subject cannot be found or contacted in spite of efforts to locate him/her before the date of his/her planned last visit, as outlined in Section 5.3.
Protocol Deviation	To be used in case of significant noncompliance with the protocol (e.g., deviation of the Inclusion/Exclusion criteria, non-compliance with time windows, blood sampling or vaccination refusal, missed injection/treatment, or error in the vaccine/treatment administration).
Withdrawal by Subject	
 
When the subject indicates unwillingness to continue in the study
 
When the subject made the decision to discontinue participation in the study for any personal reason other than an SAE/AE (e.g., subject is relocating, inform consent withdrawal, etc.)
 

# Table 5:Discontinuation Reasons

# 6. TRIAL INTERVENTION

#### 6.1 Investigational Product Description

This study will investigate the safety and immunogenicity of bivalent GI.1 and GII.4 vaccine, administered orally at total doses of  $1 \times 10^{11}$  IU/dose and  $2 \times 10^{11}$  IU/dose, for the prevention of NoV infection.

- Norovirus GI.1 Norwalk VP1 Vaccine, Oral E1-/E3-Deleted Replication Defective Recombinant Adenovirus 5 with dsRNA Adjuvant (VXA-G1.1-NN)
- Norovirus GII.4 Sydney VP1 Vaccine, Oral E1-/E3-Deleted Replication Defective Recombinant Adenovirus 5 with dsRNA Adjuvant (VXA-GII.4-NS)

VXA-G1.1-NN and VXA-GII.4-NS are E1/E3-deleted, replication-incompetent, adenovirus 5 vaccine vectors designed for use as vaccines for prevention of NoV infection. The vaccine vectors encode for a full-length VP1 gene of either Norwalk virus (VXA-G1.1-NN vaccine) or Sydney virus (VXA-GII.4-NS vaccine). In addition to the transgene cassette, a second hCMVie promoter is also present in the vaccine constructs which is used to express a ribonucleic acid (RNA) sequence that acts as an adjuvant. The adjuvant is a short hairpin RNA expressed off a promoter such that only target cells in the intestine that express antigen will also express the adjuvant. This is likely to result in a tight association of antigen with adjuvant in vivo.

The VXA-G1.1-NN and VXA-GII.4-NS vaccines are produced in tablet form. The drug substance is formulated as compressed powdered solid material containing API, tromethamine, sucrose, arginine, hydrolyzed fish gelatin (type A), and polyvinyl pyrrolidone (PVP-grade K90). The formulated and dried drug substance is blended with tableting excipients consisting of: microcrystalline cellulose, pre-gelatinized starch, magnesium stearate, and hydrophobic colloidal silica. All inactive ingredients incorporated into the drug product are generally recognized as safe (GRAS) and all are included in currently approved, US-licensed oral drug products currently listed in the FDA Inactive Ingredients Database. The formulated drug substance is compressed into tablets and enteric coated with an acetone-based solution of methacrylate polymer and talc.

The placebo for this study is manufactured similarly to the active Drug Product (DP) tablets, but without the active drug substance. The placebo tablets are indistinguishable in appearance from the active DP tablets. The number of placebo tablets dispensed to the subject will be matched to the active treatment groups. The placebo will be dispensed by the site's in-house pharmacy in a manner indistinguishable from the active treatment groups.

# 6.2 Preparation and Dispensing of Investigational Product

Investigational product doses will be prepared at the study sites by an unblinded research pharmacist(s) or designee who will be provided treatment assignment through a randomization schedule.

A trained member of the site study staff will dispense the tablet(s) constituting their assigned dose to the subject.

See the Pharmacy manual for instructions on how to prepare VXA-G1.1-NN and VXA-GII.4-NS vaccines and placebo for administration.

# 6.3 Dosing and Administration of Investigational Product

This study will investigate the safety and immunogenicity of two monovalent NoV oral tableted vaccine candidates (VXA-G1.1-NN and VXA-GII.4-NS) co-administered (bivalent delivery) against a matching placebo arm. All lots of DP will be provided as small white enteric-coated tablets for oral route of administration.

Multiple tablets of study drug will be dispensed to allow delivery of the intended vaccine dose. A matching number of placebo tablets will be dispensed to maintain the study blinding.

Intervention Name	VXA-G1.1-NN	VXA-GII.4-NS	Placebo
Туре	Biologic	Biologic	Matching placebo
Dose	Enteric-coated tablets	Enteric-coated tablets	Enteric-coated tablets
Formulation			
Dosing	Day 1	Day 1	Day 1
Schedule			
Route of	Oral		
Administration			
Administration	Subjects should fast and refrain	from ingesting solid food for at l	east 4 hours prior to oral dosing.
instructions	A trained member of the site study staff will dispense the tablet(s) constituting their assigned		
	dose to the subject. The subjects will swallow the tablets with 360 to 480 mL of water or clear		
	fruit juice (acidic, such as cranberry juice) followed by a light snack (e.g., crackers) at time of		
	dosage administration to aid in tablet transit out of the stomach. Normal food consumption may		
	resume 90 minutes after dosing. For more information refer to the study specific Pharmacy		
	Manual.		
Sourcing	Study drug will be provided to	the sites by the Sponsor or desig	nated representative.

Table 6:Investigational Product Dosing

# Table 7:Study Arm(s)

Arm Title*	Open Label Sentinel	Arm 1	Arm 2	Arm 3
Arm Type	Experimental	Experimental	Experimental	Placebo
Arm Description	Bivalent GII.4/GI.1 vaccine	Bivalent GII.4/GI.1 vaccine	Bivalent GII.4/GI.1 vaccine	Placebo
Per Strain Dose (IU)	1×10 	5×10 	1×10 	N/A
Total Dose (IU/dose)	2×10 	1×10 	2×10 	N/A

# 6.4 Formulation, Appearance, Packaging, and Labelling

Formulation:

Both the VXA-G1.1-NN and VXA-GII.4-NS are formulated as small enteric-coated tablets.

Packaging and Labelling:

The tablets are packaged into foil-sealed, high-density polyethylene (HDPE) screw-cap containers with 10 tablets per bottle.

All packaging and labeling operations for study drug will be performed according to Good Manufacturing Practices (GMP) for Medicinal Products and the relevant regulatory requirements. Label text for the study drug bottle will at a minimum include name of the manufacturer, the protocol number, the name of the product, the lot number of the product, the concentration of the vaccine, the date of manufacturing or expiration.

Secondary packaging of the study drug upon dispensing from the pharmacy to the clinical staff for subject dosing will be determined with consideration of the site' pharmacy standard operating procedures and outlined in the study pharmacy manual.

The final subject use dispensing container (cup or secondary bottle) will be appropriately labeled with specific requirements for the country and deemed necessary per the site's standard operating procedures (i.e. subject randomization number, total tablet count, dispensing date and time etc.)

## 6.5 **Product Storage and Stability**

Storage:

The Investigator will be personally responsible for product management or will designate a study site staff to assume this responsibility.

Both the VXA-G1.1-NN and VXA-GII.4-NS DP should be stored at 2-8 °C. The DP tablets may be kept at room temperature during the dispensation and administration process for a brief period. Please refer to the study specific Pharmacy Manual for detailed information.

Stability:

Stability studies have been performed on similarly formulated tablets prepared from the same or similar adenovirus 5 constructs incorporating different antigens, including, VP1 Norwalk and other influenza antigens (e.g., hemagglutinin H1). The 2-8°C data indicate that drug product potency will remain within release specification prior to retest. Additionally, data from accelerated stability studies indicate that handling at controlled room temperature or brief exposure to temperatures above room temperature (below 37°C) is acceptable for this product.

#### 6.6 Accountability Procedures

The Investigator or designee must confirm appropriate temperature conditions have been maintained during transit for study drug received and any discrepancies are reported and resolved before use of study drug.

Only subjects enrolled in the study may receive study drug and only authorized site staff may supply or administer study drug. All bottles of study drug must be stored in a secure, environmentally controlled, and monitored (manual or automated) area in accordance with the labeled storage conditions with access limited to the Investigator and authorized site staff.

The Investigator, institution, or the head of the medical institution (where applicable) is responsible for study drug accountability, reconciliation, and record maintenance (i.e., receipt, reconciliation, and final disposition records).

At the end of the study active period, the unblinded monitor will conduct a final drug reconciliation for all subjects and the study site overall. All records of study drug administration, accountability records and study drug disposition records will be examined and reconciled by the study monitor. Further details will be provided in the study specific Pharmacy Manual.

Further guidance and information for the final disposition of unused study drug are provided in the study specific Pharmacy Manual.

#### **Randomization and Blinding 6.7**

#### **Randomization Procedures** 6.7.1

#### Assignment of a Subject Number:

Each subject who signs informed consent will be assigned a subject number. Only the first 10 sentinel subjects will receive open label high dose of active vaccine ( $2 \times 10^{11}$  IU). Following SMC recommendation on review of sentinel safety data up to and including Day 8, new subjects once deemed eligible and enrolled in the study will also receive a randomization number and treatment assignment, based on the blinded randomization schedule. The subject number will be used as the primary identifier for the complete duration of the study. After the subject signs the informed

Vaxart Inc			
VXA-NVV-202	Version	2.	0

consent form (ICF), the Investigator (or designee) will enter the subject into the sites Screening Log. All screen failed and randomized subjects will have data entered in the study specific EDC.

After signing an informed consent, the subjects in the randomized double blind portion of the study will undergo screening assessments to determine study eligibility up to 45-day for Screening Period. All subjects who sign a study specific informed consent form will have data entered into the EDC. On Day 1, subjects will be randomized in a 2:2:1 ratio to one of the three treatment arms to receive active vaccine or placebo, as follows (Table 7).

## 6.7.2 Blinding Procedures

The first 10 sentinel subjects will be enrolled and receive the high dose of active vaccine in an open label manner for a safety evaluation.

If pre-established stopping rules are met, enrollment of subsequent subjects will be halted until the study SMC has completed the review of all available safety data and provides guidance regarding continuation of study.

For remaining subjects, Investigators, site personnel and the Sponsor (except as described below) will be blinded to individual subject treatment assignment.

Study drug doses will be prepared at the study sites by an unblinded research pharmacist(s) or designee who will be provided treatment assignment through a randomization schedule.

Specifically designated Sponsor representative(s) will also have access to unblinded individual subject treatment assignments for the purposes of study-required activities, including management of study drug inventory, production of summaries of data for SMC review, and performance of bioanalytical analysis. These personnel will not be directly involved in the conduct of the study.

An SMC may periodically convene to review unblinded overall safety as deemed necessary to ensure the safety of study subjects (Section 10.2).

Instructions for breaking the blind will be provided to the study site in case of a medical emergency. The Investigator has the sole responsibility for determining if unblinding of a subject's treatment assignment is warranted. Subject safety must always be the first consideration in making such a determination. The Investigator must notify the Sponsor's Medical Monitor (or designee) prior to unblinding a subject's treatment assignment. The Investigator(s) must document and report to the Medical Monitor any breaking of the treatment code but must not disclose the result of unblinding. The date and reason that the blind was broken must be recorded in the source documentation.

Appropriate personnel at the Sponsor (or designee) will unblind suspected unexpected serious adverse reactions (SUSARs) for the purpose as required per each local regulation. The Sponsor will submit SUSARs to Regulatory Agencies in blinded or unblinded fashion according to local law. The Sponsor will submit SUSARs to Investigators in a blinded fashion.

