#### Immunogenicity:

- Serum Anti-VP1 GI.1 IgA and Anti-VP1 GII.4 IgA by Meso Scale Discovery (MSD) assay by dose level
  - o geometric mean concentration (GMC) at Day 1 and Day 29
  - o geometric mean fold rise (GMFR) from Day 1 to Day 29
- Serum Anti-VP1 GI.1 IgG and Anti-VP1 GII.4 IgG by Meso Scale Discovery (MSD) assay by dose level
  - o geometric mean concentration (GMC) at Day 1 and Day 29
  - o geometric mean fold rise (GMFR) from Day 1 to Day 29
- Serum Antibody BT50 titers for both GI.1 and GII.4 by Histo-blood group antigen (HBGA) Assay
  - o geometric mean titer (GMT) Day 1 and Day 29
  - o geometric mean fold rise (GMFR) from Day 1 to Day 29

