#### 7.2 Management of Blood / Saliva / Nasal Samples

#### 7.2.1 Blood / Saliva/Nasal Sample Collection

Blood / saliva/nasal samples for the assessment of immunogenicity will be collected from the subjects as specified in the SoA (Table 1). Sample collection, storage, and shipping information can be found in the study specific Laboratory Manuals.

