#### 7.2.4 Future use of stored specimens and data

The current trial is an early phase study in which Vaxart's goal is to understand the mechanism of action of the oral NoV vaccine in the prevention of NoV illness, it is important to have samples available for the full characterization of the vaccine. The Sponsor is planning to store blood, saliva and nasal samples post the completion of the study for possible future testing towards the development of a NoV vaccine. This testing includes evaluation of serum antibody titers to NoV and cell-mediated immune responses to NoV. At this time, the exact tests are not known but this

will help to further understand how the oral NoV vaccine works in the body and in the prevention of NoV illness. Other immunological assays may be performed to further elucidate the response to our vaccine. These may include cloning the antibodies that are induced following immunization. All samples will use subject identifiers that are coded and will not include subject initials or demographic information. Only Vaxart staff will have access to the samples and data; they will be responsible for providing access to the samples as needed for assays. Samples will be stored at Vaxart or Vaxart's designee in a secured, access-controlled location for at least 05 years after the last license approval in the relevant market areas has been obtained for the vaccine being tested. Samples may be shared with collaborating researchers, but only in relationship to the NoV program. Any data developed externally will only be displayed in a deidentified form as authorized by Vaxart.

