#### **Primary Immunogenicity Assessments:**

- Serum –Anti IgA for both GI.1 and GII.4 by Meso Scale Discovery (MSD) assay by dose level
  - o geometric mean concentration (GMC) at Day 1 and Day 29
  - o geometric mean fold rise (GMFR) from Day 1 to Day 29

Vaxart Inc		
VXA-NVV-202	Version	2.0

- Serum-Antibody titers for both GI.1 and GII.4 by Histo-blood group antigen (HBGA)-Blocking Assay (BT50) –
  - o geometric mean titer (GMT) Day 1 and Day 29
  - o geometric mean fold rise (GMFR) from Day 1 to Day 29
- Serum Anti- IgG for both GI.1 and GII.4 by MSD assay
  - $\circ$  geometric mean concentration (GMC) at Day 1 and Day 29
  - o geometric mean fold rise (GMFR) from Day 1 to Day 29

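### Section 6.7.2 lets designated Sponsor representatives hold treatment codes for undefined bioanalytical work, and the protocol does not require the primary serum assays to be run and judged blind

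*Combined protocol and SAP*

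**What the plan says.** Section 6.7.2 (Blinding Procedures) gives the default for the randomized part: "Investigators, site personnel and the Sponsor (except as described below) will be blinded to individual subject treatment assignment". It then makes an exception. Designated Sponsor representatives "will also have access to unblinded individual subject treatment assignments for the purposes of study-required activities", and the listed activities are management of drug inventory, "production of summaries of data for SMC review, and performance of bioanalytical analysis". The sentence that follows adds one limit: these people are to have no direct part in conducting the study.

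The primary immunogenicity endpoints in Section 3.2.1 are serum assay results at Day 1 and Day 29. They begin with "Serum Anti-VP1 GI.1 IgA and Anti-VP1 GII.4 IgA by Meso Scale Discovery (MSD) assay by dose level" and continue with MSD IgG and the HBGA-blocking BT50 titer, each for GI.1 and GII.4. Section 8.2 lists the same three assays.

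On laboratory procedure, Section 7.2.1 says "Sample collection, storage, and shipping information can be found in the study specific Laboratory Manuals". Sections 7.2.2, 7.2.3 and 8.2 also refer to the Laboratory Manual, for preparation, processing, storage and shipment. Section 7.2.4, on future use of stored specimens, says "All samples will use subject identifiers that are coded and will not include subject initials or demographic information".

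**The concern.** Immunoassay results pass through decisions before they become data: whether a run is accepted, whether a sample is repeated, which of two readings is kept, and whether a result is excluded. If the person deciding knows the arm, those decisions can differ by arm without anyone intending it. Section 6.7.2 expressly lists bioanalytical work among the reasons for holding individual treatment codes, so the protocol contains a permission as well as a silence.

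What is at stake is the comparison of medium with high dose. Section 11.5.3 compares the two active groups descriptively on these assays, and the primary objective is to choose the dose level for Phase 3. Section 11.1 plans no hypothesis test, so the immunogenicity side of that choice rests on reading the descriptive results as they stand.

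**Working it through.** No figure in the plan needs reproducing. The check is whether any other passage closes the opening in 6.7.2.

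1. **The permission.** Access is to individual assignments, not pooled summaries. The stated purpose is the performance of bioanalytical analysis, which is broader than choosing samples for it. The documents do not define the term. The immunogenicity assays are the obvious work it could cover, but the text does not say so.

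2. **The limit in 6.7.2 itself.** The sentence keeping unblinded personnel out of direct study conduct can be read in two ways. If generating primary data counts as conducting the study, unblinded bench work is excluded. If it does not, that work is allowed. The sentence immediately before gives these people bioanalytical work as a purpose, so the exclusion is not clear. The two sentences need reconciling.

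3. **Coded identifiers (7.2.4).** Codes conceal who the subject is. They do not conceal arm from someone who also holds the assignment list. The section concerns specimens kept for later testing, so it is weak evidence in either direction on how the Day 1 and Day 29 assays are run.

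4. **Laboratory Manual (7.2.1 to 7.2.3, 8.2).** It is cited for collection, preparation, processing, storage and shipment. Blinding is not among the topics named.

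5. **SAP timing (11.5.1).** The SAP is to be final before the blind is broken for the planned analyses and is to cover data that are absent, unused or suspect. That governs the analysis. It does not expressly reach decisions at the bench.

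6. **Lock before unblinding (synopsis, 4.1, 4.4).** The Day 29 database is cleaned and locked, then the study is unblinded. This fixes when the study as a whole is unblinded. The 6.7.2 exception operates before that point and carries no timing condition.

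7. **Where judgement enters.** The Immunogenicity set in Table 9 requires a valid result after Day 1, with validity undefined. Section 11.5.3 allows results from subsets of samples without a selection rule, and relies mainly on evaluable immunogenicity sets that Table 9 does not define.

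**Reach.** All the primary immunogenicity measures come from these assays: 3 assays × 2 strains = 6. The dose comparison involves at most 50 + 50 = 100 randomized subjects; Section 11.5.3 also summarizes active against placebo (25 subjects). The 10 sentinel subjects are open label by design and fall outside the point. These counts show what could be touched, not how much bias would follow. The documents give no assay variance, repeat rate or exclusion rate from which to calculate one.

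**The case against.** The strongest reply is that 6.7.2 already contains the safeguard. Unblinded representatives may not take part directly in study conduct, every Sponsor employee not designated stays blinded, and code access may only be meant for sample selection, which has a legitimate use given the subsets in 11.5.3. This stands in part: the text does not identify assay analysts as the people holding codes. It does not settle the matter, because the listed purpose is performing the analysis and the limiting sentence is open to the reading that allows it.

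A second reply is that laboratory blinding belongs in the Laboratory Manual or the separate SAP. Neither was available, and either could contain the rule. That limits the claim to what the protocol states. A rule elsewhere would still leave 6.7.2 needing to be brought into line with it.

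Third, the readouts are numeric, the analysis is descriptive and the dose choice also rests on safety. All true, and all reasons to keep the rating low. A numeric readout does not remove decisions on repeats, exclusions and validity.

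A reader might infer that the assays will be run unblinded, or that Sponsor staff will run them because 7.2.4 restricts access to stored samples to Sponsor staff. The documents support neither. Section 6.7.2 permits code access without saying arm is visible at the bench, and the 7.2.4 restriction concerns storage for future testing. A reader might also infer that no lock precedes unblinding; Section 4.4 shows that one does.

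**Conclusion.** The point holds as a gap in wording that leaves an avoidable route to bias. Section 6.7.2 permits subject-level code access for an undefined bioanalytical purpose, its limiting sentence does not clearly exclude the primary assays, and no supplied passage requires those who run or judge the assays to be blinded to arm. It is not a finding that blinding failed or will fail, and no size of bias is claimed.

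The conclusion rests on two assumptions: that bioanalytical analysis can include the MSD and BT50 assays, and that no rule in the unseen Laboratory Manual or SAP already governs the matter. If the laboratory does work blind, the change only records existing practice. It rates as a cheap improvement.

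**What to change.** In Section 6.7.2, delete bioanalytical analysis from the purposes for which treatment codes may be held. If arm is needed to select samples, limit the purpose to that task and give it to a designated person outside the assay laboratory.

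Add a sentence stating that, for randomized subjects, staff who run the primary serum assays or decide on repeats, exclusions and validity work on coded samples and are blinded to arm until the Day 29 database lock already planned in Section 4.4. This also resolves the tension with the sentence on study conduct.

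The cost is a wording change, matched in the Laboratory Manual if it says otherwise, plus a laboratory firewall to maintain and a code-holder outside it. No visits, samples or additional locks are needed.

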#### 6.10 Concomitant Medications and Other Therapies

Concomitant medication is defined as any prescription or over-the-counter preparation.

Use of concomitant medication from 4 weeks before Day 1 through Day 29 (completion of Active Study period) must be recorded onto the eCRF from the subject's medical file along with:

- Reason for use
- Dates of administration including start and end dates
- Dosage information including dose and frequency

Medications for pre-existing medical conditions or required for a medical condition during the study are allowed if not considered exclusionary.

The Sponsor's Medical Monitor (or designee) should be contacted if there are any questions regarding concomitant or prior therapy.

Prohibited Concomitant Medication:

Medications specifically prohibited in the exclusion criteria are not allowed during the Active Study period (Section 5.1 prior/concurrent therapy), unless deemed medically necessary by the Investigator.

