# 8. TRIAL ASSESSMENTS AND PROCEDURES

Study procedures and their timing are summarized in the SoA (Table 1). Protocol waivers or exemptions are not allowed.

Immediate safety concerns should be discussed with the Sponsor immediately upon occurrence or awareness to determine if the subject should continue or discontinue study drug.

Adherence to the study design requirements, including those specified in the SoA is essential and required for study conduct.

All screening evaluations must be completed and reviewed to confirm that potential subjects meet all eligibility criteria. The Investigator will maintain a screening log to record details of all subjects screened and to confirm eligibility or record reasons for screening failure, as applicable.

Subjects who experience any serious or severe TEAEs, or any event of concern should be instructed to contact the study site and be scheduled for a visit for further evaluation. If an unscheduled visit occurs, the reason for the visit and data collected during the visit should be recorded and entered into the unscheduled eCRF.

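### Section 6.7.2 requires notice to the Medical Monitor before any code break and states no exception for a medical emergency or an unreachable contact

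*Combined protocol and SAP*

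**What the plan says.** The code-break rule for sites is one paragraph of Section 6.7.2 (Blinding Procedures). It opens by naming its subject: "Instructions for breaking the blind will be provided to the study site in case of a medical emergency". It then gives the decision to one person: "The Investigator has the sole responsibility for determining if unblinding of a subject's treatment assignment is warranted". The priority follows: "Subject safety must always be the first consideration in making such a determination". Next comes the sentence at issue: "The Investigator must notify the Sponsor's Medical Monitor (or designee) prior to unblinding a subject's treatment assignment". After that there is a separate reporting duty: "The Investigator(s) must document and report to the Medical Monitor any breaking of the treatment code but must not disclose the result of unblinding". Source documents must also record when and why the blind was broken.

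Earlier in the same section, doses are described as "prepared at the study sites by an unblinded research pharmacist(s) or designee who will be provided treatment assignment through a randomization schedule". Someone at the site therefore holds the assignment, although the text does not name that person as the emergency route.

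Three other places bear on how strictly the sentence reads:
- Section 8 states: "Protocol waivers or exemptions are not allowed".
- Section 14.6 counts any departure from the protocol as a deviation.
- Section 12.7 has the Investigator tell the Sponsor immediately of urgent measures taken to protect subjects from an immediate hazard.

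**The concern.** The paragraph is written for emergencies, yet its notification step is unconditional and comes before the code break. It does not limit the step to cases where contact is feasible, allow notice afterwards, or say what to do if neither the Medical Monitor nor a designee can be reached. A site that follows it to the letter would contact the Sponsor before opening the code, even when the Investigator has already decided that the assignment is needed at once. A site that opens the code first would have a deviation to record.

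At stake is the speed of access to the assignment for a subject in an emergency, and the position of an Investigator who must choose between the literal rule and the safety-first sentence. No endpoint, sample size or analysis is affected.

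**Working it through.** No arithmetic applies beyond the count of subjects covered. The check sets the sentences side by side and looks for an exception.

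1. **Who is covered.** The randomized arms in Section 4.1 (Table 3) are 50 + 50 + 25 = 125 subjects. The 10 sentinel subjects are open label and have no code to break.

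2. **For how long.** Sections 4.1 and 4.4 say the study is unblinded once all subjects have completed the Day 29 visit and the database has been cleaned and locked. The rule therefore matters from dosing until then, not through the Day 365 follow-up.

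3. **What the sentence requires.** The verb is mandatory and the order is explicit: notice first, code break second. A designee may receive the notice. No approval, agreement or reply is asked for, and no form of contact is prescribed.

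4. **Set against sole responsibility.** A duty to tell someone does not transfer a decision. The two sentences are compatible.

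5. **Set against the safety-first sentence.** That sentence governs whether to unblind. It does not address the order of notice and code break. The two do not contradict each other directly, but they pull apart when contact takes time: the decision has been made on safety grounds, and acting on it must still wait for a notification.

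6. **Search for an exception.** None was found in the supplied text.
   - Section 8 rules out waivers and exemptions. It introduces the trial procedures and may be aimed mainly at those, but its wording has no such limit.
   - Section 14.6 makes unblinding before notice a deviation on its plain wording, whatever the reach of Section 8.
   - Section 6.10 shows that the protocol writes a carve-out when one is intended: prohibited medication is barred "unless deemed medically necessary by the Investigator". Section 6.7.2 has no counterpart.

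7. **Set against Section 12.7.** That section contemplates acting on an immediate hazard and informing the Sponsor of measures already taken, which is the reverse of the order in Section 6.7.2. It is general and does not mention unblinding, so it cannot safely be read as lifting the prior-notice step. It does show that the two sections should be reconciled.

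8. **What prior notice adds.** The reporting duty already ensures that the Medical Monitor learns of every code break, and the bar on disclosing the result protects the blind. What prior notice adds is the chance to discuss a break before it becomes irreversible. That benefit is kept if prior notice remains the default wherever it costs no time.

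**The case against.** The strongest reply is that the sentence asks for very little. It requires notice and not permission, a designee will do, and a message might satisfy it. Section 8 already expects immediate safety concerns to be discussed with the Sponsor at once, so contact would be under way in any case. The site's code-break instructions are a separate document that was not supplied, and they may say what to do when nobody answers. Each subject takes a single dose on Day 1, so the assignment cannot inform any decision about further doses. Section 6.9 says that no specific antidote for overdose is known. The documents identify no emergency in which the assignment would change care.

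Most of this stands, and it limits the point. A reader might infer several stronger things that the documents do not support:
- **That the Sponsor controls the decision, or that the paragraph contradicts the Investigator's sole responsibility.** It does not, because notice is all that is required.
- **That delay is established.** It is an inference. No contact time, form of notice or availability arrangement is given.
- **That this is the only emergency code-break rule.** That cannot be said without the site instructions.
- **That prior notice serves no purpose.** It allows discussion before an irreversible step.

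The reply does not supply the missing exception. If the site instructions contain one, they would conflict with an unconditional protocol sentence, and the sentence would still need correcting. Nor does Section 12.7 settle the matter, since it does not mention unblinding.

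**Conclusion.** The point holds as a minor defect of wording. Section 6.7.2 makes prior notice mandatory for every code break and states no exception for an emergency or an unreachable contact. Followed literally, it can hold back emergency access to the code, and unblinding first would be a deviation. The difficulty is one of timing and a missing exception. It is in tension with the safety-first sentence and with Section 12.7, but it does not contradict the allocation of responsibility to the Investigator.

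The rule reaches 125 randomized subjects for the blinded period only, and expected use is low. The size of any delay cannot be derived from the documents. The conclusion assumes that the sentence is read as written and that no unsupplied document overrides it.

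**What to change.** Reword the notification sentence in Section 6.7.2 along these lines: *Where it causes no delay, the Investigator informs the Medical Monitor (or designee) before unblinding. Otherwise the Investigator may unblind without prior contact and must inform the Medical Monitor as soon as possible afterwards, without disclosing the assignment.* Keep the existing duties on documentation and non-disclosure, and put the same rule in the code-break instructions given to sites, so that the two agree with each other and with Section 12.7.

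The cost is one sentence in the protocol and a matching edit to the site instructions. The downside is that in rare cases the Sponsor hears of a code break after it has happened and loses the chance to discuss it first. The existing reporting duty still ensures that the Sponsor is told.
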